2.5.1.2 Secondary Endpoints

Secondary outcomes will be improvement in functionality and quality of life based on the KOOS Function in Sport and Recreation KOOS, and Quality of Life Scale at 6 months as well as the quantitative functional measures and changes in medication use. To adjust for multiple comparisons, the Holm-Bonferroni correction method will be implemented.

2.5.2 Sample Size Determination

The Knee Injury and Osteoarthritis Outcome (KOOS) Score which is a primary outcome measure is a measure of patients' knee and associated problems and functionality. It is endorsed by the American Academy of Orthopedic Surgeons, the US Food and Drug Administration, and the International Cartilage Repair Society and has demonstrated reliability for both clinical and research purposes (11). The Visual Analog Scale (VAS) for pain will be used as a secondary outcome measure. This scale is also well-validated and has demonstrated reliability for patients with osteoarthritis (12). The Minimal Clinically Important Difference (MCID) for KOOS has been reported to be ~10. Data on the KOOS indicates a population standard deviation of 15 (koos.nu). Assuming we wish to detect an MCID of 10 points in this population, our targeted effect size is 0.66. A power calculation for a paired t-test (baseline vs 6-month KOOS Pain scores) shows our pilot study of 15 patients would have 22% power.

2.5.3 *Efficacy Analysis*

Comparison of semi-quantitative and quantitative outcome measures will be performed with the appropriate statistics testing. For the pilot group, baseline and endpoint scores will be compared using paired t-tests.

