Study Title: Geniculate Artery Embolization for the Treatment of Knee Osteoarthritis 04/08/2025

G190248 Supplement 001

A. Cover Page

Device Information : Device name: Teleflex Gel-Bead

Intended use of device:

The Gel-Bead embolization particles will be used to perform geniculate artery embolization (GAE) for the purposes of treatment of osteoarthritis-related knee pain.

Device Information:

Device name: Teleflex Gel-Bead

Intended use of device:

The Gel-Bead embolization particles will be used to perform geniculate artery embolization (GAE) for the purposes of treatment of osteoarthritis-related knee pain.

Sponsor-Investigator and Correspondent Contact Information:

[name] University of Pittsburgh Medical Center [name] [contact] / [contact] [contact]

Manufacturer Information:

Teleflex (acquired Vascular Solutions, Inc. February 2017) [name] [contact]

Distributed by Medtronic

Referenced files: There are no referenced files.

Protocol Ammendments:

Updated protocol to remove 6-minute walk test due to feasibility issues in performing

B. Clinical Plan

The primary goal of our investigation is to determine if geniculate artery embolization (GAE) will result in a decrease in pain and disability caused by knee osteoarthritis. The investigation will be conducted as two distinct studies:

 A pilot study of GAE for the treatment of knee osteoarthritis
 A series of up to 30 subjects undergoing geniculate artery embolization will be included in this arm with the explicit purpose to demonstrate safety and efficacy.

The primary endpoint of this study is overall efficacy of treatment as determined by a minimal clinically significant improvement in KOOS pain score of 10 based on the KOOS Pain questionnaire at 6 months.

Secondary outcomes will be improvement in functionality and quality of life based on the KOOS Function in Sport and Recreation, and KOOS Quality of Life Scales. Secondary outcomes will also include changes in quantitative functional metrics as well as reduction in medication use.

Technical success will be defined as the performance of diagnostic angiography of the knee with delivery of the Gel-Bead particles to a region of hypervascularity within the knee resulting in reduced flow/occlusion of the target vessels. Clinical success will be defined by a decrease in pain of 10 points per the KOOS questionnaire at 6 months.

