2.2.1 General Study Design

A series of 15 patients undergoing geniculate artery embolization will be included in this arm with the explicit purpose to demonstrate safety and efficacy.

This trial will assess reduction in pain, functional improvement, and reduction of conservative medical therapy in patients with mild to moderate knee osteoarthritis who have failed conservative

management, for 6 months and for up to two years following embolization.

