2.3.1 General characteristics of the proposed subject population

Similar to prior studies conducted on GAE, subjects included in the study will be those with mild to moderate knee osteoarthritis with moderate to severe pain that is refractory to conservative management. These are patients who have significant symptoms but are not ideal candidates for total knee replacement.

2.3.2 *Anticipated number of research subjects*

For the Pilot Study, 30 patients are expected to enroll (defined as completion of the informed consent process as per University IRB policies) and all are expected to complete the study.

2.3.3 Inclusion Criteria:

1. Patients between ages 18 and 75 with moderate/severe knee pain secondary to primary osteoarthritis. Moderate/severe pain will be defined as pain 30 mm to

100 mm on the Visual Analog Pain Scale (where 0 denotes 'no pain' and 100 mm denotes worst pain imaginable')

- 2. Grade 1, 2, or 3 osteoarthritis on the Kellgren-Lawrence grading scale on knee x-ray in the last 12 months
- 3. Pain must be refractory to 3 months of medical management (which may include a combination of oral analgesics, intraarticular steroids, viscosupplementation, opioid therapy, etc)
- 4. Patients willing and able to consent to the study

2.3.4 Exclusion Criteria:

- 1 Kidney dysfunction defined as an estimated GFR < 60 mL/min
- 2 Acute knee injury
- 3 Current local infection
- 4 Prior ipsilateral knee replacement surgery
- 5 Infectious or inflammatory arthritis
- 6 History of contrast allergy resulting in anaphylaxis
- 7 INR (International Normalization Ratio) > 1.6
- 8 Platelets < 50,000
- 9 Significant atherosclerosis that would limit angiography
- 10 Active malignancy
- 11 Active pregnancy
- 12 Appropriate candidate for knee replacement surgery determined by clinical and physical examination
- 13 Recent within 3 months, or active cigarette user
- 14 Any other condition that in the opinion of the investigator would preclude the patient from participation.

2.4 Study Procedures:

2.4.1 Patient Recruitment:

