3.0 Risk Analysis

3.1 Anticipated Risks

To mitigate risk to patient confidentiality, data will be kept in encrypted files on a secure UPMC server. The identifying patient information will be kept in a second document separate from the clinical data gathered, and a non-identifying code will be assigned to each patient. The data collected will not be shared with any person(s) not included in the study investigator list. Should a breach of conduct occur, the IRB will be notified immediately by one of the principal investigators.

Participants in the intervention arm will undergo an invasive procedure and will be subjected to moderateto-high risk. Risks include but are not limited to bleeding at the puncture site, infection, damage to nearby structures, synovitis, worsening of groin hematoma, and nontarget embolization. A qualified, boardcertified interventional radiologist will perform the procedure. Sterile technique will always be followed. Radiation exposure to the patient will be minimized using standard strategies (e.g. aggressive collimation, minimizing fluoroscopy time). All adverse events will be thoroughly documented and reported to the UPMC IRB immediately.

Because the study population has osteoarthritis-related knee symptoms refractory to conservative management, the next treatment option traditionally available is knee replacement surgery. Transarterial embolization, while still an invasive procedure, has a much lower risk profile that knee replacement surgery.

This trial will include 15 initial patients to confirm safety and initial efficacy of the treatment. Patients will include both male and female and range from age 18-75 who meet the inclusion criteria as detailed above. GAE will be performed by the trained investigating Interventional Radiologists who have significant experience in performing endovascular embolization procedures.

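### The stated 22% power does not belong to the paired t-test described (the plan's own effect size gives about 67% at 15 patients and 94% at 30), and the sample size is given as both 15 and 30

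*Combined protocol and SAP*

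**What the plan says.** Section 2.5.2 takes a minimal important difference of about 10 KOOS points and a population SD of 15, and continues: "Assuming we wish to detect an MCID of 10 points in this population, our targeted effect size is 0.66". It names a paired t-test of baseline against 6-month KOOS Pain as the basis of the power calculation, and reports that this "shows our pilot study of 15 patients would have 22% power". Section 2.5.3 confirms the test: "For the pilot group, baseline and endpoint scores will be compared using paired t-tests".

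The number of patients appears in five places:

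- Section B, Clinical Plan: "A series of up to 30 subjects undergoing geniculate artery embolization will be included in this arm"
- Section 2.2.1: "A series of 15 patients undergoing geniculate artery embolization will be included in this arm"
- Section 2.3.2: "For the Pilot Study, 30 patients are expected to enroll", with no losses anticipated
- Section 2.5.2: 15, in the power statement
- Section 3.1: "This trial will include 15 initial patients to confirm safety and initial efficacy of the treatment"

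Section 2.5.1.1 calls for a two-sided test but writes the hypotheses as a comparison of GAE and sham means. No sham arm is described anywhere in the document.

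**The concern.** An effect size of two-thirds of an SD, tested within patients on 15 pairs, should give power well above one half, so 22% looks wrong on sight. It is the only power figure in the document, and demonstrating efficacy is a declared purpose of the study. An IRB or regulator who takes 22% at face value would conclude that the study can barely detect its own target difference and that a null result would say almost nothing. The plan's own inputs do not support that reading.

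The power statement also uses 15 patients, while Section 2.3.2 expects 30. With both numbers in force, a reader cannot tell which one the calculation should support, how many people will undergo an invasive procedure, or when enrolment is complete.

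**Working it through.** **Inputs.** From Section 2.5.2: difference 10, SD 15, effect size d = 0.66 (10/15 = 0.667), n = 15, paired t-test. From Section 2.5.1.1: two-sided. From Section 2.3.2: n = 30. The 5% level is an assumption; Section 2.5.4 states it only for adverse-event comparisons.

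**1. The plan's figure, by the plan's method.** For a paired t-test, the degrees of freedom are n − 1 and the noncentrality is d√n. Power is the probability that a noncentral t variable falls beyond the two-sided critical value.

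| n | d | Noncentrality | Critical t | Power |
|---|---|---|---|---|
| 15 | 0.66 | 0.66 × √15 = 2.556 | 2.145 | 66.2% |
| 15 | 0.667 | 0.667 × √15 = 2.582 | 2.145 | 67.1% |
| 30 | 0.66 | 0.66 × √30 = 3.615 | 2.045 | 93.7% |
| 30 | 0.667 | 0.667 × √30 = 3.651 | 2.045 | 94.2% |

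The 22% is not reproduced.

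**2. Other readings of the same test.** A one-sided test at n = 15 gives 78.4% to 79.1%. A normal approximation (two-sided, d = 0.667) gives 73.3%. To bring the paired test down to 22% by tightening the level would take a two-sided alpha of about 0.003, which the plan does not mention.

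**3. SD 15 as a single-visit SD.** A paired test needs the SD of the change. If 15 is the SD at each visit and r is the correlation between baseline and 6 months, then SD of change = 15 × √(2(1 − r)). This equals 15 only when r = 0.5.

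| r | SD of change | Power, n = 15 | Power, n = 30 |
|---|---|---|---|
| 0 | 21.2 | 40% | 70% |
| 0.3 | 17.7 | 53% | 85% |
| 0.5 | 15.0 | 67% | 94% |
| 0.7 | 11.6 | 87% | 99.5% |

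Solving the paired test at n = 15 for 22% power gives d = 0.328, so SD of change = 10/0.328 ≈ 30.5. The largest SD of change that two visits with SD 15 allow is 15 × √4 = 30, at r = −1, and power there is 22.5%. No admissible correlation brings power down to exactly 22%.

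**4. A calculation that does give 22%.** For an unpaired two-sample t-test with group sizes 7 and 8, df = 13 and noncentrality = d × √(7 × 8/15). With d = 0.66 this is 1.275 and power is 21.9%. With d = 0.667 it is 1.288 and power is 22.3%. So 22% matches 15 patients divided between two groups. This fits the GAE-versus-sham hypotheses in Section 2.5.1.1, but that origin is an inference; the document does not state it.

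**5. Sample size.** Section B and Section 2.2.1 use almost the same sentence, one with a ceiling of 30 and the other with 15. Section 2.3.2 expects 30 to enrol. Section 3.1 calls its 15 patients initial, which hints at a first tranche, but no section sets out a stage, an interim look or a rule for moving from 15 to 30.

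**The case against.** The strongest counter-argument is that 67% and 94% are conditional too. The plan calls 15 a population SD and gives neither a correlation nor an SD of change, and the 5% level is not stated for the primary test. At r = 0 the figure for 15 patients is 40%, so the understatement is then a factor of about 1.8 (40/22) rather than 3 (67/22). This stands as a limit on the replacement number. It does not rescue the 22%, which lies outside everything the stated SD allows.

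The 94% also needs 30 evaluable patients, although Section 2.4.2.1 withdraws anyone who significantly escalates conservative therapy. As an illustration, 24 evaluable patients would give 88% at r = 0.5 and 60% at r = 0. Moreover, the paired test asks only whether the mean change differs from zero in an uncontrolled series. It is not power for the comparison with sham written in Section 2.5.1.1. Both points are fair, and they limit what a corrected figure can be said to show.

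On sample size, a ceiling of 30 and 15 initial patients need not contradict each other. But Section 2.2.1 (15) and Section 2.3.2 (30) do conflict, and nothing in the document reconciles them.

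Finally, this is a pilot, its size is not derived from power, no decision rule uses the 22%, and the error understates the design. That lowers the practical harm. The sponsor nevertheless chose to report a power figure, and that figure belongs to a different test.

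**Conclusion.** Both parts of the concern hold. The 22% is wrong for the paired t-test that Sections 2.5.2 and 2.5.3 specify. Applying the plan's own effect size directly, power is 66% to 67% at 15 patients and about 94% at 30, roughly three and four times the stated value. These figures assume a two-sided 5% level, an SD of change of 15 (equivalent to r = 0.5 if 15 is a single-visit SD) and complete follow-up. Over r from 0 to 0.7 the ranges are 40% to 87% at 15 patients and 70% to 99.5% at 30. The conclusion that 22% is wrong holds for any correlation, while the exact replacement depends on the SD of change. The planned number of patients is separately inconsistent and must be settled before any single power figure can be quoted.

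**What to change.** 1. Choose one sample size and state it in Section B and in Sections 2.2.1, 2.3.2, 2.5.2 and 3.1. If 15 is meant as a first stage of 30, describe the stage and the rule for continuing.
2. Delete the 22%. Restate Section 2.5.2 along these lines: paired t-test of baseline against 6-month KOOS Pain, two-sided alpha 0.05, mean change 10, SD of change 15 (a correlation of 0.5 if 15 is the single-visit SD), power 67% at n = 15 or 94% at n = 30, whichever n is adopted.
3. Add a short table of power over the SD of change, such as the one above, and state that n means evaluable patients.
4. Say that this is power to detect a non-zero mean change within patients, so that it is not read as power for a sham comparison.

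The cost is protocol wording: one recalculated figure, one small table and one reconciled sample size. Correcting the power statement does not itself call for more patients, visits or assessments.

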- 5. There are no signs of active bleeding or hemorrhage
- 6. Patient has a safe ride home

After GAE, follow-up will occur at 1 week (\pm 4 days), 1 month (\pm 2 weeks), 3 months (\pm 2 weeks), 6 months (\pm 2 weeks) from the date of treatment.

Visit 3 - 1 week (± 4 days) Post Procedure Phone Call

One week after the GAE procedure, a phone follow-up call will be made to check the on status of the subject. Standard post surgical questions pertaining to infection and pain will be asked. If there are any concerns, an in-person evaluation will be scheduled.

Visit 4 - 1 month (± 2 weeks) Post Procedure

Subjects will have the following assessments performed:

- Physical examination including vital signs
- KOOS and VAS questionnaires
- 30 second chair stand test
- Review of adverse events

Visit 5 - 3 months (± 2 weeks) Post Procedure

Subjects will have the following assessments performed:

- Physical examination including vital signs
- KOOS and VAS questionnaires
- 30 second chair stand test
- Review of adverse events

Visit 6 - 6 months (± 2 weeks) Post Procedure

Subjects will have the following assessments performed:

- Physical examination including vital signs
- KOOS and VAS questionnaires
- 30 second chair stand test
- Review of adverse events

Whenever possible, follow-up phone calls\tele-medicine visits will be made to subjects at 12 and 24months post procedure to obtain updated information on pain.

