2.4.2.1 Study Compliance

Subjects will be required to avoid escalation of conservative therapy during the study period. A review of current and prior conservative treatment measures will be reviewed with each subject during follow-up visits. Any patient that significantly elevates conservative therapy (e.g. initiation of a new medication or therapy not previously used) will be withdrawn from the study.

Early Withdrawal of Subjects:

Subjects will be withdrawn from the study under the following conditions:

- 1 At any point at the patient's discretion
- 2 Any major complication that occurs that prevents the ability to perform/complete the GAE procedure
- 3 Patient is unable to complete at least one follow-up visit

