2.5 Statistical Methods and Data Analysis

2.5.1 Study Endpoints

2.5.1.1 Primary Endpoints

The primary endpoint of this study will be overall efficacy of treatment as determined by an improvement in pain of at least 10 points based on the KOOS Pain questionnaire at 6 months. The null and alternative hypotheses respectively will be: H_0 : Mean_{GAE} = Mean_{Sham} and H_A : Mean_{GAE} \neq Mean_{Sham}, with a two sided test.

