2.5.4 Safety Analysis

Differences in the occurrence of adverse events between groups will be assessed with chi-square tests with a significance level p < 0.05. Descriptive statistics will be used to report occurrence of adverse events in the pilot group.

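### The only stated efficacy test, a paired t-test at 6 months, leaves out anyone without a 6-month score and makes no use of the 1- and 3-month KOOS Pain scores

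*Combined protocol and SAP*

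**What the plan says.** - **Endpoint.** Section 2.5.1.1 defines efficacy as "improvement in pain of at least 10 points based on the KOOS Pain questionnaire at 6 months". The Clinical Plan uses the same 10-point criterion for clinical success.
- **Method.** Section 2.5.3 names one specific test for the pilot group: "baseline and endpoint scores will be compared using paired t-tests". The power text in section 2.5.2 sets the two time points as baseline and 6 months. The other sentence in 2.5.3 promises only suitable tests and names none.
- **Data.** "KOOS and VAS questionnaires" are listed at Visits 4, 5 and 6 (1, 3 and 6 months), and KOOS is also taken at screening.
- **Loss.** Section 2.4.2.1 begins its withdrawal rule with "Any patient that significantly elevates conservative therapy". It also allows withdrawal at the patient's wish, and for a patient who cannot complete at least one follow-up visit. Section 2.3.2 expects every patient to complete.
- **What is absent.** The plan has no imputation rule, defined analysis population, repeated-measures model, missing-data section or sensitivity analysis.

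**The concern.** A paired t-test needs both scores from the same patient. A patient who is doing badly at 3 months and then leaves, or is withdrawn for escalating therapy, contributes nothing to the result, although up to three KOOS Pain scores may already be on file. Patients in most pain are the likeliest to escalate, so those who reach 6 months are probably a better-than-average group.

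The study has one arm, so no control group with similar loss exists to offset this. The bias passes directly into the estimate of efficacy. Changing the withdrawal rule would not fully remove the problem, because patients may still leave at their own wish.

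**Working it through.** **Inputs from the documents.** SD 15, target change 10 points and effect size 0.66 (section 2.5.2). The sample size is 15 (sections 2.2.1, 2.5.2 and 3.1), up to 30 (Clinical Plan) or 30 (section 2.3.2).

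**Assumptions.** The documents give no loss rate and no within-patient correlation. I take 20% loss, correlation r from 0.5 to 0.7 and equal correlation between visits, and read 15 as the SD of a single score. Section 2.5.1.1 calls for a two-sided test without giving its alpha. The only stated level, 0.05, belongs to the adverse-event comparison (2.5.4), so 0.05 is also an assumption.

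**Step 1: the plan's own figure.** For a paired t-test with n = 15 and d = 0.66, df = 14 and noncentrality = 0.66 × √15 = 2.56, which gives 66.2% power. The stated 22% is not reproduced. A two-sample test with 7.5 patients per arm gives 22.0%, so the figure looks like a two-group calculation. That is a separate matter, and nothing below depends on it. Loss also lowers paired-test power: 15 falling to 12 gives 55.0%, and 30 falling to 24 gives 87.2%.

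**Step 2: size of the bias in a large sample.** Let the missing 20% be drawn at random from the worst 40% on change from baseline.
- The mean of the lowest 40% of a standard normal is −0.966, so completers sit at 0.966 × 0.2/0.8 = +0.2415 SD.
- The SD of change is 15 × √(2(1 − r)): 15.0 at r = 0.5 and 11.6 at r = 0.7.
- With equal correlations, the 3-month and 6-month changes correlate at 0.5.
- Loss following the 3-month change: 0.2415 × 0.5 × 15.0 = 1.8 at r = 0.5, and 0.2415 × 0.5 × 11.6 = 1.4 at r = 0.7.
- Loss following the 6-month change: 0.2415 × 15.0 = 3.6 at r = 0.5, and 0.2415 × 11.6 = 2.8 at r = 0.7.

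**Step 3: simulation at n = 15 and 30.** The likelihood estimate uses all four scores.

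| Loss depends on | Completers' bias | Likelihood bias |
|---|---|---|
| 3-month score | +1.3 to +1.8 | about 0 |
| 6-month change | +2.7 to +3.5 | +1.8 to +2.3 |

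In the second row the share removed is (2.7 − 1.8)/2.7 = 33% to (3.5 − 2.3)/3.5 = 34%. With no missing data the two estimates are identical.

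**Step 4: overall accuracy.** RMSE = √(bias² + SD²). These runs use a true change of 10 and 20% loss. The patients lost have the highest values of a score that adds poor 3-month change and random noise in equal parts.

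| n, r | Completers | Likelihood |
|---|---|---|
| 15, 0.5 | √(1.69² + 4.37²) = 4.69 | √(0.10² + 4.48²) = 4.48 |
| 15, 0.7 | √(1.32² + 3.31²) = 3.56 | √(0.04² + 3.44²) = 3.44 |
| 30, 0.5 | √(1.76² + 3.04²) = 3.51 | √(0.02² + 3.05²) = 3.05 |
| 30, 0.7 | √(1.43² + 2.32²) = 2.73 | √(0.04² + 2.35²) = 2.35 |

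The gain is small at 15 patients and clearer at 30. With loss completely at random both estimates are unbiased, and at n = 15, r = 0.5 the SDs are 4.30 and 4.26. The case therefore rests on bias, with little gain in precision.

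**The case against.** The strongest reply is that the model's advantage depends on how patients are lost. When loss is driven by the observed 3-month score, a likelihood estimate is unbiased by construction. Escalation is triggered by pain at the time, which may arise between months 3 and 6 or before the 3-month score exists. A reader might infer that the interim scores would correct most of the bias. The documents do not support that: they say nothing about when or why patients will be lost, and in the second scenario about two thirds of the bias remains. This objection stands, and the fix needs a sensitivity analysis that does not assume missing at random. The paired t-test cannot serve as that analysis, because it carries the bias in question.

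Three further points stand in part.
- An unstructured covariance for four visits has 10 parameters besides 4 means, which is demanding with 15 patients. Coverage and convergence of that exact model were not tested, so a fallback is needed.
- A model of mean change does not yield the 10-point responder result. Section 2.5.1.1 also states a comparison with a sham group that the present design does not have, and that conflict must be reconciled.
- The plan does not say that patients without a 6-month score are dropped. That follows from a paired test with no imputation rule.

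Section 2.3.2 does expect full completion. That is an expectation, however, and section 2.4.2.1 of the same plan provides for withdrawals.

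**Conclusion.** The point holds as a recommended improvement. The one efficacy method that the plan specifies uses only patients with both baseline and 6-month scores, and the plan's own withdrawal rule makes selective loss likely.

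Under the stated assumptions, the completers' mean change is too high by 1.3 to 1.8 points (13 to 18% of the 10-point target) if loss follows the 3-month score, and by 2.7 to 3.5 points (27 to 35%) if it follows the 6-month score. The repeated-measures estimate has lower bias and lower RMSE in both cases, but it nearly removes the bias only in the first.

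It would go too far to call the paired t-test invalid. With complete data it gives the same 6-month estimate, and with loss unrelated to outcome it is unbiased. The size of the harm depends on a loss rate and a correlation that the documents do not give.

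**What to change.** 1. Make the primary estimate of mean 6-month KOOS Pain change a likelihood-based repeated-measures model. Use the baseline, 1-, 3- and 6-month scores of all patients in whom GAE was attempted, with visit as a categorical factor and Kenward-Roger degrees of freedom. Specify unstructured covariance, and name in advance the simpler structure to use if it does not converge.
2. Keep the paired t-test as a supporting analysis.
3. Add one missing-not-at-random sensitivity analysis, for example missing 6-month scores set to the patient's baseline, or a delta shift applied to the model's predictions.
4. For the 10-point endpoint, count patients without a 6-month score as non-responders.

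**Cost.** A little more analysis work and slightly wider error bars at n = 15 (SD of the estimate 4.37 against 4.48 in the first row of the accuracy table). No new visits, patients or data are needed.
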